10.5 Vital Signs and Other Observations Related to Safety

10.5.1 Vital signs

The following vital signs measurements will be assessed:

- Systolic Blood Pressure (mmHg)
- Diastolic Blood Pressure (mmHg)
- Pulse Rate (bpm)
- Temperature (C)
- Body weight (kg)

The following summaries will be provided:

- A summary of the absolute and change from AS0008 Baseline for each vital sign variable at each visit, by treatment group at the completion of AS0008 and overall.
 - This summary will include the derived BMI at each time point.

- A summary of the number and percentage of subjects experiencing at least 1 on-treatment markedly abnormal value), as defined in **Table 10–13**, for a vital sign variable during the treatment period (excluding any measurements that occurred prior to the first administration of study medication in AS0009 or more than 140 days after the last administration of study medication) by treatment group at the completion of AS0008 and overall (based on change from AS0008 Baseline).

Table 10–13: Definitions of markedly abnormal blood pressure values

Variable (Unit)	Markedly abnormal low	Markedly abnormal high
Systolic blood pressure (mmHg)	<90 and a decrease from AS0008 Baseline of ≥ 20	>180 and an increase from AS0008 Baseline of ≥ 20
Diastolic blood pressure (mmHg)	<50 and a decrease from AS0008 Baseline of ≥ 15	>105 and an increase from AS0008 Baseline of ≥ 15

Vital signs measurements, including age, sex, race, weight and flags to identify markedly abnormal values, will be listed. The listing will include the derived BMI at each time point.

10.5.2 **Electrocardiograms**

A summary of the number and percentage of subjects with normal, abnormal not clinically significant and abnormal clinically significant ECG results by visit will be presented by treatment group at completion of AS0008 and overall.

The following ECG variables will be summarized by visit (absolute values and change from AS0008 Baseline), by treatment group at completion of AS0008 and overall:

- PR interval (ms)
- RR interval (ms)
- QRS duration (ms)
- QT interval (ms)
- QTcF interval (ms)
- QTcB interval (ms)

Outliers in QTcF and QTcB are defined as values meeting the following criteria at any on-treatment assessment in AS0009:

- QTcF or QTcB >450 ms OR
- QTcF or QTcB change from AS0008 Baseline >30 ms

Outliers will be summarized using the following categories:

- Values >450 ms, >480 ms and >500 ms
- Increase from AS0008 Baseline of >30 ms, >60 ms and >90 ms
- Value >450 ms AND increase from AS0008 Baseline of >30 ms

- Value >500 ms AND increase from AS0008 Baseline of >60 ms

The summary will include the number and percentage of subjects who meet the criteria above at any on-treatment (scheduled or unscheduled) assessment (excluding any measurements that occurred prior to the first administration of study medication in AS0009 or more than 140 days after the last administration of study medication).

All ECG variables will be listed, including unscheduled and repeat visits, if applicable. A separate listing of ECG findings will be presented together with the interpretation (normal, abnormal not clinically significant, or abnormal clinically significant).

10.5.3 Other safety variables

Assessment of Tuberculosis

Scheduled TB laboratory test results will be included in the laboratory data listings. Results of unscheduled TB testing at local laboratories will be listed separately. The response to the first question of the 'Evaluation of signs and symptoms of tuberculosis' questionnaire will be listed.

[figure not shown]
Electronic Columbia Suicide Severity Rating Scale

The electronic Columbia-Suicide Severity Rating Scale (eC-SSRS) is a standardized and validated instrument developed for the assessment of the severity and frequency of suicidal ideation and behavior ([Posner et al, 2011](#); [Mundt et al, 2010](#)).

Suicidal ideation is defined as an event in any of the following 5 categories:

Suicidal behavior is defined as an event in any of the following 4 categories:

Suicidal ideation or behavior is defined as an event in any of the above 9 categories.

Self-injurious behavior without suicidal intent will also be reported.

The eC-SSRS can be administered to assess suicidal ideation and behavior over a lifetime, or since the last time it was assessed. The intent in this OLE study was to assess suicidal ideation and behavior since the last time it was assessed and refer back to the lifetime assessment conducted at the start of AS0008. However, some subjects completed the 'lifetime' assessment (in error) at one or more visits in AS0009 and recorded positive responses to some questions. Based on a review of their original lifetime assessment in AS0008, these positive responses are

not considered to represent a change in suicidal ideation and behavior during the study. The summary tables will include only the ‘since last assessment’ responses; all responses will be listed.

The incidence of subjects with suicidal ideation, suicidal behavior, suicidal ideation or behavior and self-injurious behavior at least once for any on-treatment assessment (including unscheduled assessments, but excluding any measurements that occurred prior to the first administration of study medication in AS0009 or more than 140 days after the last administration of study medication) during AS0009, will be summarized by treatment group at completion of AS0008.

eC-SSRS data will be listed.

Health Care Provider Consultations

Out-patient non-protocol health care provider consultations will be listed.

Extra-articular assessments

Extra-articular assessments performed after the AS0009 EV will be listed separately for the SS.

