9. Subject develops laboratory abnormalities (with or without clinical symptoms) of alanine aminotransferase (ALT) or aspartate aminotransferase (AST) as defined in [Section 6.3.1](#); neutrophils $<0.5 \times 10^9/L$ (neutropenia); lymphocytes $<0.5 \times 10^9/L$ (lymphopenia). Any laboratory value or change judged to be clinically significant by the Investigator should prompt consideration of whether the subject should continue on IMP. For clarification, laboratory values that are markedly abnormal as per [Table 17-1](#) and [Table 17-2](#) will be flagged to the Investigator and to the medical monitor but do not trigger mandatory withdrawal unless listed above. (Refer to [Section 6.3.1](#) for withdrawal criteria in relation to potential drug-induced liver injury [PDILI].)
10. Subject has active suicidal ideation as indicated by a positive response (“Yes”) to questions 4 or 5 or to the suicidal behavior questions of the “Since Last Visit” version of the self-rated electronic Columbia-Suicide Severity Rating Scale (eC-SSRS). The subject should be referred immediately to a Mental Healthcare Professional and must be withdrawn from the study.
11. Subjects with a HADS-D score ≥ 15 must be withdrawn. Any subject who has a HADS-D score of >10 should be referred immediately to a Mental Healthcare Professional for further evaluation and potential withdrawal by the Investigator.
12. Subjects with newly diagnosed IBD or with IBD flares during the study must:
 - Be referred, as appropriate, to a health care professional treating IBD, such as a gastroenterologist
 - Discontinue IMP and be followed-up until resolution of active IBD symptoms

If IBD flares increase in severity or frequency during the study, the Investigator should use clinical judgment in deciding whether the subject should continue in the study and contact the Medical Monitor and UCB study physician to confirm the subject's suitability for continued participation in the study.

All subjects who withdraw from the study due to an AE must be followed until resolution of the event or until the event is considered stable. All subjects who withdraw from the study due to development of a laboratory abnormality must be closely monitored.

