9.1.3 Other safety topics of interest

Pre-specified safety topics of interest for the study are: infections (serious, opportunistic, fungal, and TB), neutropenia, hypersensitivity, suicidal ideation and behavior, depression, major cardiovascular events, liver function test changes/enzyme elevations, malignancies, and inflammatory bowel diseases (with gastroenterology referral, as appropriate). This is based on findings from the IMP clinical program to date, potential risks generally associated with biologic immunomodulators, or findings from other medicines with a related mechanism of action. There are no specific AE reporting requirements for these topics, however special monitoring, additional data collection activities, and/or enhanced signal detection activities (within UCB) are in place.

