13.3 Planned safety analyses

13.3.1 Safety analyses

Safety variables will be analyzed for all subjects in the SS.

Adverse events will be coded according to the Medical Dictionary for Regulatory Activities.

Adverse events will be summarized descriptively by treatment group at completion of the lead-in study, primary system organ class, high level term, and preferred term. This summary will include raw incidence rates, exposure adjusted incidence rate (EAIR) with associated 95% confidence interval, and the exposure adjusted event rate (EAER), where the EAIR and EAER are expressed per 100 patient-years of exposure.

Patient exposure at risk in days will be defined as date of last administration of bimekizumab - date of first administration of bimekizumab +20 weeks. If a subject has an adverse event with fatal outcome, patient exposure at risk is censored at the date of death.

The extent of exposure to IMP in AS0009 will be summarized using descriptive statistics by treatment group at AS0009 entry.

Change from AS0009 entry values in laboratory and vital signs variables will be summarized descriptively by visit and by treatment group at completion of the lead-in study.

The results of the eC-SSRS will be summarized by visit and by treatment group at completion of the lead-in study using number of subjects and percentages with events in: each of the eC-SSRS questions, suicidal behavior, suicidal ideation, suicidal behavior and ideation, and self-injurious behavior without suicidal intent.

All safety analyses will be conducted for both subpopulations.

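### The SAP drops the protocol's by-visit, by-question eC-SSRS summary and does not declare the change

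*SAP*

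**What the plan says.** Protocol 13.3.1 defines the analysis: "The results of the eC-SSRS will be summarized by visit and by treatment group at completion of the lead-in study". The numbers and percentages of subjects are to be given for "each of the eC-SSRS questions, suicidal behavior, suicidal ideation, suicidal behavior and ideation, and self-injurious behavior without suicidal intent".

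SAP 10.5.3 specifies one summary, by treatment group at completion of AS0008: "The incidence of subjects with suicidal ideation, suicidal behavior, suicidal ideation or behavior and self-injurious behavior at least once for any on-treatment assessment". It is confined to AS0009 assessments from the first dose to 140 days after the last. It uses only the 'since last assessment' form of the questionnaire, because some subjects completed the lifetime form in error. Beyond that summary, "all responses will be listed".

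Protocol 6.3, criterion 10, makes a positive answer "to questions 4 or 5 or to the suicidal behavior questions" a reason for withdrawal. Questions 4 and 5 are therefore singled out by the protocol itself.

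SAP 3.10 gives seven changes to protocol-defined analyses, plus the COVID-19 additions in 3.10.1. None concerns the eC-SSRS. SAP 13 (Amendments 1 to 3) does not mention it either.

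**The concern.** The primary objective is long-term safety, and suicidal ideation and behavior is one of the safety topics that protocol 9.1.3 names in advance. A graded instrument given about every 12 weeks for four years can show whether positive answers cluster early or late, and how severe they are. An at-least-once incidence over the whole treatment period shows neither. Within the ideation row, a subject with the mildest positive answer counts the same as one who answers yes to question 4 or 5.

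Visit-level denominators also matter. Because some subjects completed the wrong form at some visits, the number of usable assessments can differ from visit to visit. A by-visit table would show this; a pooled incidence hides it.

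The procedural side is separate. The protocol defined this table, and a reader who relies on SAP 3.10 to learn what changed would not find out that it had gone.

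**Working it through.** The plan gives no figure to reproduce. The check compares the two texts and counts the assessments.

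**Comparison**

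| Feature | Protocol 13.3.1 | SAP 10.5.3 |
|---|---|---|
| Treatment group at end of lead-in | yes | yes |
| By visit | yes | no |
| Each question | yes | no (listed only) |
| Ideation | yes | yes, at least once |
| Behavior | yes | yes, at least once |
| Ideation and behavior combined | yes | yes, as ideation or behavior, at least once |
| Self-injury without suicidal intent | yes | yes, at least once |

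The aggregate categories survive as four separate rows. What is lost is the visit dimension and the question dimension.

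**Is the change declared?** SAP 3.10 covers change from entry, the laboratory baseline, maintenance of response, the FAS, randomized-group summaries, the NSAID subgroup and sub-population safety tables. The nearest entries in SAP 13 are a general update of outputs for AEs of special interest (Amendment 1) and an added table of neuropsychiatric TEAEs by event type (Amendment 2). Both concern adverse events, not eC-SSRS responses. The change is not declared.

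**Number of assessments affected** (schedule tables, protocol 5.2 and SAP 2.3)

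- Entry: 1
- Weeks 4 and 8: 2
- Weeks 12 to 204 every 12 weeks: (204 − 12)/12 + 1 = 17
- Week 208: 1
- Safety follow-up: 1

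Total = 1 + 2 + 17 + 1 + 1 = 22 including entry, and 22 − 1 = 21 after entry. Entry precedes the first AS0009 dose, so it is not on-treatment and does not enter the SAP's rates. The 21 is a maximum: follow-up is due at 20 × 7 = 140 days with a window of −3/+7 days, and the SAP excludes assessments more than 140 days after the last dose.

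**What is compressed.** SAP 10.5.3 refers to 5 ideation and 4 behavior categories, 5 + 4 = 9, plus self-injurious behavior. Over up to 21 assessments these become four rates per treatment group.

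**Does another summary fill the gap?** SAP 10.2.3 tabulates adjudicated neuropsychiatric events by type: completed suicide, attempt, preparatory acts, ideation and two non-suicidal types. Ideation is a single code there, with no visit and no question level, and the source is adverse events. It does not replace the eC-SSRS table.

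**The case against.** The best defense is that nothing is lost. Every response is listed, and SAP 3.1 sorts by-subject listings by visit where applicable, so a reader could count question 4 or 5 answers by hand. Behavior, the other part of criterion 10, has its own rate. The adjudicated table grades neuropsychiatric events, and discontinuations are summarized by primary reason. No primary or secondary variable depends on the eC-SSRS. All of this stands, and it limits the weight of the point. It does not answer it: a listing gives no rates or denominators, the discontinuation table does not isolate the trigger, and the protocol promised a table.

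Some stronger readings are tempting and should not be drawn.

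- *The SAP collapses everything into one rate, or severity cannot be seen in any summary.* It keeps four categories, and the adjudicated event table separates degrees of severity. The gap is confined to summaries of eC-SSRS data.
- *Subjects reaching the withdrawal trigger cannot be counted.* They can be, from the listings; they are simply not tabulated.
- *The SAP has no depression analysis, and that is a second undeclared change.* Protocol 9.1.3 does name "suicidal ideation and behavior, depression, major cardiovascular events" among its topics, and none of the eight topics in SAP 10.2.3 is depression. But the same protocol section states that "There are no specific AE reporting requirements for these topics", and protocol 13 defines no depression TEAE table and no count at the HADS-D limits in criterion 11 (above 10, or 15 and above). There is no protocol-defined analysis to depart from. HADS-D change and normal HADS status are summarized by visit (SAP 8.3), and depression preferred terms would fall in the general TEAE tables (SAP 10.2).

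**Conclusion.** The point holds for the eC-SSRS alone. SAP 10.5.3 omits the by-visit and by-question counts that protocol 13.3.1 requires, and the omission is undeclared. The consequence is that no eC-SSRS summary shows timing or distinguishes question 4 or 5 ideation from milder ideation, across up to 21 assessments after entry. It should be corrected, but it puts no primary or secondary result at risk.

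Depression is at most an optional note: a named safety topic without a matching topic table, partly covered elsewhere.

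The conclusion assumes that SAP 10.5.3 describes all planned eC-SSRS summaries. The section refers to summary tables in the plural but specifies only the at-least-once incidence. If table shells outside these documents include a by-visit table, the SAP should say so. The category names missing from the public copy of 10.5.3 were not counted against the plan.

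**What to change.** In SAP 10.5.3:

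1. Restore the protocol table: number and percentage of subjects with a positive response, by visit and by treatment group at completion of AS0008, for each eC-SSRS question and each aggregate category. Use 'since last assessment' responses only, and show the number of subjects with such a response at each visit as the denominator.
2. Keep the at-least-once summary and add question-level rows, so that questions 4 and 5 can be read directly.
3. If any part is left out on purpose, list it in SAP 3.10 with the reason.

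Optionally, add a sentence to SAP 10.2.3 saying where depression is reported, since protocol 9.1.3 names it as a topic.

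The cost is one by-visit table and some extra rows in an existing one. The data are already collected and already listed. No visit, assessment or clinical rule changes.

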10.5.4 Comments

A listing of comments will be presented, based on the ES. This listing will include comments received from the laboratory vendors (including safety laboratory data, PK and ADAb data).

This document cannot be used to support any marketing authorization application and any extensions or variations thereof.

12 APPENDICES

12.1 Data Handling Rules for ASAS20, ASAS40 and ASAS5/6 Response

The rules for handling missing data in relation to defining the achievement of ASAS20 and ASAS40 responses are provided in [Table 12-1](#). This table also indicates, where appropriate, the imputation as a non-responder (DTYPE = WC) in the analysis datasets for the NRI analyses. For tables presented on OC data, the data selected will include all instances where DTTYPE is not populated in the analysis datasets.

Table 12-1: Data Handling Rules for ASAS20 and ASAS40

Components	Component Status	ASAS ^a	DTYPE
4 components present	3 or more components improved ≥40% and ≥2 units AND no deterioration in remaining component	Y	
4 components present	3 components improved ≥40% and ≥2 units AND remaining component deteriorated ≥20% and ≥1 unit	N	
At least 1 component present	1 or more component(s) has deteriorated ≥20% and ≥1 unit	N	
3 components present	3 or more components improved ≥40% and ≥2 units	Y	
3 components present	2 components improved ≥40% and ≥2 units AND no deterioration in remaining component(s)	N	WC
3 components present	1 or 0 components improved ≥40% and ≥2 units AND no deterioration in remaining component(s)	N	
2 components present	2 or 1 components improved AND no deterioration in remaining component(s)	N	WC
2 components present	0 components improved	N	
1 or 0 components present	1 or 0 components improved ≥40% and ≥2 units AND no deterioration in remaining component(s)	N	WC

^a Rules are based on ASAS40, similar rules will be implemented for ASAS20 response where improvement is defined as a change ≥20% and ≥1 units.

WC = worst case.

Similar rules for defining the achievement of ASAS5/6 response are presented in [Table 12-2](#).

Table 12-2: Data Handling Rules for ASAS5/6 Response

Components	Component Status	ASAS	DTYPE
6 components present	5 or more components improved $\geq 20\%$	Y	
6 components present	4 or fewer components improved $\geq 20\%$	N	
5 components present	5 components improved $\geq 20\%$	Y	
5 components present	4 components improved $\geq 20\%$	N	WC
5 components present	3 or fewer components improved $\geq 20\%$	N	
4 components present	4 or 3 components improved $\geq 20\%$	N	WC
4 components present	2 or fewer components improved $\geq 20\%$	N	
3 components present	3 or 2 components improved $\geq 20\%$	N	WC
3 components present	1 or 0 component(s) improved $\geq 20\%$	N	
2 components present	2 or 1 components improved $\geq 20\%$	N	WC
2 components present	0 component(s) improved $\geq 20\%$	N	
1 or 0 components present	1 or 0 components improved $\geq 20\%$	N	WC

WC = worst case.

